organs, Cohort 2 (300 µg; 7.4 GBq/cycle; cumulative 22.2 GBq; [Table 2](#)) will be initiated (see priority classification in [Figure 2](#)). However, if improved safety regarding DLTs is seen with increased peptide mass, Cohort 2 (300 µg; 7.4 GBq/cycle; cumulative 22.2 GBq) may be delayed until experience is gained with the 7.4 GBq dose at the higher peptide mass (700 µg). If optimal peptide mass is evaluated to be >300 µg then this cohort will not be opened.

Intra-individual peptide mass dose evaluation (Cohorts 3 and 6 – Part B)

Cohorts 3 and 6 will allow the intra-individual evaluation of peptide mass. In both Cohorts 3 and 6, subjects will receive the same cumulative radioactivity as in Part A (4.5 GBq/cycle; cumulative, 13.5 GBq; [Table 2](#)). The associated peptide mass dose will also be the same (300 µg) in Cycles 1 and 3, and will be increased to 700 µg in Cohort 3 and 1300 µg in Cohort 6 during Cycle 2.

Peptide mass dose escalation (Cohorts 4 and 5 and optional Cohorts 7 and 8 – Part B)

In Cohort 4, subjects will receive 6 GBq/cycle (cumulative 18 GBq) with a peptide mass dose of 700 µg, for three cycles ([Table 2](#)). After one cycle, if no safety signal is observed in Cohort 4, Cohort 5 will be initiated. In Cohort 5, subjects will receive 7.4 GBq/cycle (cumulative, 22.2 GBq) with a peptide mass dose of 700 µg, for three cycles ([Table 2](#)).

Cohorts 7 and 8 will be cancelled if ssr2 saturation is seen with peptide mass dose of 700µg and 1300 µg in Cohort 3 or 6 and/or if there are other safety signals ([Table 2](#)). There will be no further dose escalation of OPS201 peptide after 1300 µg.

The dose escalation rules

The DRB will consist of a team of “permanent” decision makers (the core team), including selected principal investigators and Ipsen personnel. All final decisions will be made by the core team. The number of DRB meetings may change as needed and the DRB can be called upon rapidly if there is a safety issue of concern in a cohort. The aim is to have all meetings via conference call, but if the timing does not allow for this, then the meeting can be conducted via email exchange or two conference calls with split attendees. A DRB charter will be developed with further details. Ad-hoc DRBs can be convened at any time during the trial.

Dose escalation (peptide mass dose and radioactivity, see [Figure 2](#)) will primarily be decided based on the clinical and safety data of the subjects.

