At each PRRT cycle (Visits 1 to 3 and additional cycles, if any) the study medication will be administered after the conduct of a safety examination of the subject. The IRPP (20 mL of $^{177}\text{Lu-OPS201}$) will be administered by an i.v. infusion at a rate of 10 mL/h over 120 minutes. Infusion rate modification (up or down) would be under the investigator's judgement and may be temporarily halted or even further slowed down if the subject does not tolerate the IRPP infusion. The overall infusion duration should not exceed 4 hours.

Note: Prior to adoption of the protocol version 8.0, infusion was to be administered over 30 to 60 minutes.

Prophylaxis may be considered if the subject is thought to be at increased risk of infusion-related reactions as per the site's standard of care. Appropriate treatment should be administered should an infusion-related reaction occur including somatostatin analogues. At any time, if infusion-related reactions are encountered, the infusion should be slowed or interrupted.

Duration of treatment:

The estimated core trial duration of Part A is 18 to 21 months (for all subjects) including 6 to 10 months of treatment for a single subject, while the long-term follow-up will last for up to 2 years after the EOCT/EW Visit. The estimated core trial duration of Part B is 14 to 20 months (for all subjects) including 6 to 10 months of treatment for a single subject, while the long-term follow-up will last for up to 2 years after the EOCT/EOAC/EW Visit. After the long-term follow-up period is completed, all subjects will be invited to participate in a safety surveillance study.

Reference therapy, dose and mode of administration:

Not applicable

Criteria for evaluation (endpoints):**Safety endpoints**

- Frequency and/or descriptive summaries of standard safety and tolerability parameters: AEs (including SAEs) according to National Cancer Institute (NCI) Common Terminology Criteria for Adverse Events (CTCAE) v5.0 and vital signs, laboratory tests (haematology, biochemistry and urinalysis, and pituitary markers), 12-lead and Holter electrocardiogram (ECG), DLTs, physical examination results and use of concomitant medication throughout the study

Biodistribution and radioactive PK of the radiopharmaceutical endpoints

- Maximal uptake (%) at the target lesions
- Maximal uptake (%) in discernible organs and blood
- Area under the curve (AUC) of ¹⁷⁷Lu-OPS201 in discernible thoracic and abdominal organs, target lesions and blood

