3.1.3 Justification for Part B Design

In animal experiments, no saturation of the sstr2 was observed when higher peptide mass doses were administered in a xenograft mouse model.[39] Nevertheless, the effect of the increasing peptide mass dose and the peptide mass at which lesion receptor saturation occurs in humans is unknown. The extrapolation from animal experiments may be limited by the fact that, in these

xenografts, receptor density was relatively high in comparison to normal distribution of receptors in the mouse.

Receptor saturation by the peptide is predicated on:

- (a) the number of receptors in nontumoural tissue (physiological expression) and
- (b) tumour burden and related sstr2 density (total receptor burden).

Regardless of tumour type, the higher the receptor burden the more peptide maybe required before saturation occurs. It is therefore important that the peptide masses being studied in this protocol are evaluated for sstr2 saturation. Hence Cohorts 3 and 6 will evaluate the peptide mass and specifically if receptor saturation has occurred, starting with 300 µg for Cycle 1, then increasing to 700 µg and 1300 µg respectively for Cycle 2 before repeating the 300 µg dosing for Cycle 3 (see [Figure 13](#)). Thus, the tumour-to-background dose ratio, and the tumour-to-bone-marrow dose ratio, using imaging dosimetry, can be evaluated in the same subjects. In these cohorts, administering 4.5 GBq/cycle, which was shown to be tolerated in Part A of the study, will allow comparison of intra-subject variability of the uptake due only to the peptide mass. It also allows Cohort 3 to start in parallel to Cohort 1 which is the next logical increase in dosing at 300 µg (6 GBq per cycle) following Part A.

The other cohorts in Part B will be initiated in a staggered manner after gaining experience with previous cohorts, thereby allowing safer investigation at higher radioactivity and/or higher peptide mass dose. If tumour sstr2 saturation is observed, then the lower peptide dose will be confirmed. Therefore, Cohorts 7 and 8 will be cancelled if the peptide saturation is seen in Cohorts 3 and/or 6. Similarly, Cohort 2 may be cancelled if a peptide mass dose range of 700 µg to 1300 µg is found to be optimal.

Subject numbers

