9.3 Pharmacokinetics of the OPS201

9.3.1 Blood Sample Collection

Part B only. Blood samples (2 mL) for assessment of OPS201 plasma levels will be collected at the following time points (at Visit 1 only):

At Visit 1 (first infusion): before the infusion (baseline), at the end of the infusion (0), 5 \pm 1 minute, 30 \pm 3 minutes, 60 \pm 5 minutes and at 4 hours \pm 10 minutes, 6 hours \pm 30 minutes, 8 hours \pm 30 minutes, 24 \pm 1 hours and 48 \pm 1 hours after the administration of ^{177}Lu -OPS201.

Blood samples should be collected from the arm opposite to that of the study drug infusion, or from another site.

The accurate time of sample collection must be recorded. Any issues associated with sample collection or processing should be reported to the sponsor's monitor.

Complete instructions for sample collection, processing, handling and shipment will be provided in the laboratory manual.

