9.3.2 Urine Sample Collection

To determine the renal excretion of OPS201, the concentration of OPS201 in urine will be determined.

The samples for urine OPS201 concentration analysis will be taken from urine collected during three different periods at Cycle 1 only: from 0 (start of the infusion) to 4, 4 to 24 and 24 to 48 hours after the start of infusion (0 (start of the infusion) to 4 hours only for US and Canada sites).

The accurate time of urine collection and the total urine volume for each collection interval must be recorded. Any issues associated with sample collection or processing should be reported to the sponsor's monitor.

Complete instructions for urine collection, processing, handling and shipment will be provided in the laboratory manual.

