All AEs and SAEs occurring during the Screening period and more than 6 months after the last dose of study medication will be listed and flagged as occurring before or after (during period 3) the active phase of the study; however, these will not be defined as TEAEs.

TEAEs will be summarised by study part, cohort (part B only) and overall with the number and percentage of subjects with adverse events classified by primary system organ class and preferred term. The number of occurrences of a TEAE will also be presented. The summary of AEs will also be repeated by time period. A listing of AEs by time period will also be presented.

In addition, summary tables will also be presented for SAEs, TEAEs related to ¹⁷⁷Lu-OPS201, TEAEs related to OPS301, treatment emergent ¹⁷⁷Lu-OPS201 related SAEs, OPS301 related SAEs, TEAEs leading to premature discontinuation of study medication, TEAEs leading to dose delays, TEAEs leading to dose reduction, TEAEs leading to dose interruption, TEAEs per decreasing frequency, TEAEs by associated NCI CTC worst grade and by causality. There will also be a separate summary for Adverse Events of Special Interest (AESI) which will be defined as any TEAE related to ¹⁷⁷Lu-OPS201 which occurs the day of ¹⁷⁷Lu-OPS201 administration (same date as ¹⁷⁷Lu-OPS201 administration and at any cycle).

Summary tables of adverse events will be provided with the number and percentage of subjects with adverse events classified by primary system organ class, preferred term (ordered alphabetically) and associated CTCAE version 5.0 worst grade. In the event of multiple occurrences of the same adverse events being reported by the same subject, the maximum intensity (Grade 5 > Grade 4 > Grade 3 > Grade 2 > Grade 1 > missing > not applicable) and the most serious causality (related > not related) will be chosen.

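### Cohorts 3 and 6 yield no OPS201 peptide PK at 700 or 1300 µg, and the AESI, DLT and TEAE summaries described in the SAP pool their one higher-mass infusion with those at 300 µg

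*Protocol*

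**What the plan says.** **Peptide mass.** For Cohorts 3 and 6 the synopsis states: "The associated peptide mass dose will also be the same (300 µg) in Cycles 1 and 3". Protocol Table 11 shows 700 µg (Cohort 3) or 1300 µg (Cohort 6) at Cycle 2 only, and 300 µg again at any additional Cycles 4 and 5. Radioactivity is 4.5 GBq throughout.

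**Purpose.** Protocol 3.1.3: "Hence Cohorts 3 and 6 will evaluate the peptide mass and specifically if receptor saturation has occurred". The comparison is to be made within subject, by imaging dosimetry.

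**OPS201 PK.** Plasma (Protocol 9.3.1): "Blood samples (2 mL) for assessment of OPS201 plasma levels will be collected at the following time points (at Visit 1 only". Urine (Protocol 9.3.2): "three different periods at Cycle 1 only". The schedule footnotes in Protocol Table 8 agree.

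**Adverse events.** SAP 3.2.1.2: "TEAEs will be summarised by study part, cohort (part B only) and overall with the number and percentage of subjects with adverse events". It repeats the summary by time period, but the periods are counted from the last dose. SAP 3.2.1.1 summarises DLTs by part, cohort, whether radioactivity was adapted, and overall. SAP 3.2.1.2 defines an AESI as a related TEAE on an administration date at any cycle, and specifies no split by cycle.

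**Infusion time.** It is now 120 minutes. Before protocol version 8.0, "infusion was to be administered over 30 to 60 minutes".

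**The concern.** The optimal peptide mass is a secondary objective (Protocol 2.2). The second study hypothesis (2.3) expects higher mass to improve the tumour-to-background ratio, with a possible safety benefit. Cohorts 3 and 6 are the only cohorts that change mass within a subject at constant radioactivity. The second interim analysis, run after they complete, is meant to confirm the peptide dose and settle whether Cohorts 2, 7 and 8 open (Protocol 11.6).

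Two parts of the evidence do not reach the cycle that carries the contrast. Cold-peptide PK is measured one cycle too early. The clinical event summaries described in the SAP add the Cycle 2 infusion to the 300 µg infusions in the same subjects. Infusion-day reactions matter most here, because Protocol 8.1.12 names hypersensitivity to the intravenous peptide as a risk, and infusion duration changed during the study as well.

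**Working it through.** **The plan's own figure.** Protocol 11.2 gives, for n = 8 and a 30% SD of the paired difference, 80% power for a 2-fold and 99% for a 3-fold change. Reading 30% as 0.30 on the log10 scale, with a normal approximation:

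- Power = Φ(log10(fold) × √8 / 0.30 − 1.96)
- 2-fold: Φ(2.838 − 1.960) = 81.0%
- 3-fold: Φ(4.498 − 1.960) = 99.4%

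This matches the plan, although the documents do not state that scale. A two-sided paired t test on the same inputs gives 68.4% and 96.9%. The figure does not bear on the two gaps below.

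**1. OPS201 profiles by mass at Visit 1** (masses from Protocol Table 11, cohort sizes from Protocol 3.1.2)

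| Mass at Visit 1 | Cohorts | Profiles |
|---|---|---|
| 300 µg | 1, 3, 6 | 3+8+8 = 19 to 5+10+10 = 25 |
| 300 µg | 2 (optional) | 3 to 5 |
| 700 µg | 4, 5 | 3+3 = 6 to 5+5 = 10 |
| 1300 µg | 7, 8 (optional) | 0 if not opened, otherwise 6 to 10 |

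- Cohorts 3 and 6 contribute none above 300 µg.
- Protocol 3.1.3 expects 10 + 10 + 5 = 25 subjects in Cohorts 3, 6 and 1, which equals the Part B minimum. SAP Table 9 (DRB-B) holds Cohort 4 until those three are fully recruited. If Part B ends there, the study has no profile above 300 µg.
- At the full 40, Protocol 3.1.3 allots three subjects to each remaining cohort: 6 profiles at 700 µg and 6 at 1300 µg.
- Cohorts 3 and 6 at 20 subjects are 20/25 = 80% to 20/40 = 50% of Part B.

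**2. What sampling at Visit 2 would take** (Protocol 9.1.1 against 9.3.1)

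- OPS201 plasma times: predose, 0, 5 min, 30 min, 1 h, 4 h, 6 h, 8 h, 24 h, 48 h (ten).
- Blood already drawn at Visit 2 for radioactivity: predose, 0, 1 h, 4 h, 24 h, 48 h, 72–96 h, 144–168 h.
- Shared times: six. New times: 5 min, 30 min, 6 h, 8 h.
- Extra blood if all ten are added: 10 × 2 mL = 20 mL. Against the 563.5 mL Part B total in Protocol Table 9, that is 20/563.5 = 3.5%.
- Yield: 8 to 10 profiles at 700 µg and 8 to 10 at 1300 µg, each paired with 300 µg if Visit 1 sampling is kept.

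**3. What a cohort-level event figure can show.** Over three core cycles, one infusion of three is at the higher mass; with additional cycles, up to four are at 300 µg. Period 1 in SAP 3.2.1.2 runs from treatment to 56 days after the last dose, so every infusion falls inside it.

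Illustration only, since the documents give no event rates. Assume independent infusions, with AESI risk a per 300 µg infusion and b per higher-mass infusion. The proportion of subjects with at least one AESI is 1 − (1 − a)²(1 − b).

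- a = 5%, b = 30%: 1 − 0.9025 × 0.70 = 36.8%
- a = b = 14.2%: 1 − 0.858³ = 36.8%
- a = 20.5%, b = 0: 1 − 0.795² = 36.8%
- a = 0, b = 36.8%: 36.8%

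The same cohort figure fits any higher-mass risk from 0 to 36.8%.

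**The case against.** A reader might infer that neither PK nor safety at the higher mass can be read from Cohorts 3 and 6. The documents do not support that.

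- **Radioactive PK and dosimetry are measured at Cycle 2.** Blood radioactivity is sampled at Visits 1 to 3 (Protocol 9.1.1), as are whole-body and five-point SPECT/CT images (9.2). SAP 3.2.2 summarises blood AUC by cycle and forms Visit 2 to Visit 1 and Visit 2 to Visit 3 absorbed-dose ratios. This is the stated purpose of these cohorts, and receptor saturation is covered. What is missing is OPS201 by mass spectrometry, because blood radioactivity measures total ¹⁷⁷Lu.
- **OPS201 PK is an exploratory objective** (Protocol 2.2), although Protocol 3.2.2.3 lists it among secondary endpoints. This lowers the stakes but does not fill the gap.
- **Some safety output is by cycle.** Grade 3/4 haematology and biochemistry are tabulated by cycle (Protocol 11.4.10), and nadir is summarised by cycle (SAP 3.2.1.3). Time since last dose is derived for adverse event listings (SAP Appendix 1). An AESI falls on an infusion date by definition, so a careful reader of the listings could place each one.
- **Constant-mass cohorts help at 700 µg.** Cohorts 4 and 5 are not optional, and Cohort 1 against Cohort 4 compares 300 and 700 µg at 6 GBq between subjects.
- **The table list in SAP Appendix 2 is not visible**, so a by-cycle event table cannot be ruled out.

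A reader might also infer that the board lacks the Cycle 2 DLT counts that SAP Table 9 calls for. The board works from a data set set out in its own charter (SAP 3.2.17), so that does not follow.

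These points narrow the concern to cold-peptide PK and the grouping of clinical events. On those two, the visible text offers no answer.

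**Conclusion.** The point holds in two limited parts.

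- **PK.** Cohorts 3 and 6 give no OPS201 profile at 700 or 1300 µg. The study total is 6 to 10 at 700 µg if Cohorts 4 and 5 run, none at 1300 µg unless Cohort 7 or 8 opens, and none above 300 µg if Part B stops at Cohorts 1, 3 and 6. These counts rest on the cohort sizes and masses in the protocol; how many cohorts opened is not stated.
- **Event summaries.** As described in the SAP text, the AESI, DLT and TEAE summaries for these cohorts mix peptide masses within subject. The data to separate them are already collected. This conclusion is conditional on the unseen table list.

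By-cycle tables will not isolate a mass effect on delayed events, because Cycle 2 also carries more cumulative radioactivity than Cycle 1, and the return to 300 µg at Cycle 3 helps only in part. Same-day AESIs can be assigned to an infusion. The change is worth making, but the primary purpose of these cohorts does not depend on it.

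**What to change.** **1. SAP tables, Cohorts 3 and 6.**

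- Tabulate same-day AESIs per infusion by cycle and peptide mass, with the number of infusions at each mass as denominator. Show infusion duration (30–60 against 120 minutes).
- Tabulate DLTs and TEAEs by cycle of onset, meaning the cycle of the last infusion before onset. Add a footnote that delayed events are confounded with cumulative radioactivity.

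The cost is programming only, and it applies to every subject already treated.

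**2. OPS201 plasma at Visit 2**, for subjects in Cohorts 3 and 6 not yet past that visit, by a short amendment and an entry in the separate PK analysis plan. There are two options:

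- *Move* the samples from Visit 1. No extra OPS201 sample volume is needed. The downsides are less 300 µg PK (Cohort 1 still supplies it) and loss of the paired comparison.
- *Add* them to Visit 1. This keeps the pairing, at about 20 mL more blood per subject.

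Either option brings the 5-minute, 30-minute, 6-hour and 8-hour draws to Visit 2. Check the added volume against the per-visit and one-month ceilings in Protocol 5.1 and 5.3.

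Visit 2 urine is optional. No urine is collected for PK at that visit now, so it would be a new collection of up to 48 hours. If all subjects are already past Visit 2, only the first change remains available, and the study report should say that peptide PK at the higher masses was not measured in these cohorts.

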9.3.2 Urine Sample Collection

To determine the renal excretion of OPS201, the concentration of OPS201 in urine will be determined.

The samples for urine OPS201 concentration analysis will be taken from urine collected during three different periods at Cycle 1 only: from 0 (start of the infusion) to 4, 4 to 24 and 24 to 48 hours after the start of infusion (0 (start of the infusion) to 4 hours only for US and Canada sites).

The accurate time of urine collection and the total urine volume for each collection interval must be recorded. Any issues associated with sample collection or processing should be reported to the sponsor's monitor.

Complete instructions for urine collection, processing, handling and shipment will be provided in the laboratory manual.

9.3.3 Analytical Procedures

Plasma and urine samples will be analysed to determine concentrations of OPS201 using a high-performance liquid chromatography (HPLC) with tandem mass spectrometric (MS/MS) detection, according to a separate protocol established with the dedicated analytical laboratory. Residual plasma and urine used for OPS201 PK analysis may also be used for exploratory analysis. CCI

Plasma and urine samples remaining from the analysis may be retained by the sponsor for additional investigations (i.e. long-term stability, reproducibility).

CCI

10 EXPLORATORY BIOMARKERS AND BIOBANKING

10.1 Exploratory Biomarkers

CCI

CCI

CCI

11 STATISTICS

Detailed methodology for summary and statistical analyses of the data collected in this study are documented in a statistical analysis plan (SAP), v1.0 Final which is dated and completed on 09 March 2017 (revisions may be made to this to incorporate changes made to methodology of Part B in the protocol v6.0 and up). The SAP may modify the plans outlined in the protocol; however, any major modifications of the primary endpoint and/or its analysis will also be reflected in a protocol amendment.

Statistical evaluation will be performed using Statistical Analysis System (SAS)[®] (v9.2 or higher)

11.1 Analyses Populations

Subjects will be assigned to each analysis set prior to the statistical analysis. The following population will be used during statistical analyses:

- **Screened Subjects Set:** all subjects screened (i.e. who signed the informed consent)
- **Eligible Subjects Set:** all subjects who comply with the inclusion and exclusion criteria (according to the investigator/site) and have entered the study (performed the Screening Visit).
- **Safety Analysis Set:** all subjects who received study medication.
- **Intent-to-Treat Set (ITT):** all subjects in the Eligible Subjects Set who received study medication.
- **Per-Protocol Set (PP):** all subjects in the ITT Set who complete the study according to the protocol with no major protocol deviation. Any protocol deviation will be evaluated by the sponsor based on the individual case. Major protocol deviations will be defined in the Protocol Deviations Document and identified in a data review meeting before database lock.
- **Intent-To-Treat Dosimetry Analysis Set (ITT-DAS):** all subjects in the ITT Set for whom at least one complete set of dosimetry imaging and dosimetry blood sample measurements is available.
- **Per-Protocol Dosimetry Analysis Set (PP-DAS):** all subjects in the ITT-DAS for whom no major protocol violations occurred affecting dosimetry variables.
- **Radiopharmaceutical Pharmacokinetic Set:** For Part A and Part B, all subjects in the ITT Set who receive at least one dose of study medication and have at least one measured radioactive concentration in blood.

- **OPS201 Pharmacokinetic Set (for Part B only):** all subjects in the ITT Set who receive at least one dose of study medication and have no major protocol deviations affecting the PK variables and who have a sufficient number of OPS201 levels to estimate the main PK parameters (i.e. C_{max} , T_{max} , and AUC).

